4 PLANNED ANALYSES

No formal interim analysis will be conducted.

There will be analysis performed for exploratory purposes as per sponsor discretion.

At no point will the results of the analysis have an impact on the study design with an absence of stopping rules for efficacy and futility.

A Final Analysis is planned for the whole study period (including screening period, study intervention period and follow-up period).

Document: \\ieedc

 $vnasc01\\BIOSdata\\Sanofi\\Fabrazyme\\IAB16602\\Biostatistics\\Documentation\\SAP\\SAP\\Sanofi\\Final\\AB16602\\Biostatistics\\Documentation\\SAP\\SAP\\SANOfi\\Final\\AB16602\\Biostatistics\\Documentation\\SAP\\SAP\\SANOfi\\Final\\AB16602\\Biostatistics\\Documentation\\SAP\\SAP\\SANOfi\\Final\\AB16602\\Biostatistics\\Documentation\\SAP\\SAP\\SANOfi\\Final\\AB16602\\Biostatistics\\Documentation\\SAP\\SAP\\SANOfi\\Final\\AB16602\\Biostatistics\\Biostat$

[figure not shown]
Version\lps17726-16-1-9-sap.docx

[figure not shown]
Author: Version Number: Final V1.0

Version Date: 22Oct2024

Template No.: CS_TP_BS016 Revision 7 Reference: CS_WI_BS005

Effective Date: 01Nov2021

Page 24 of 65

4.1 FINAL ANALYSIS

A Final, planned analyses identified in this SAP will be performed by IQVIA Biostatistics following Sponsor Authorization of this Statistical Analysis Plan, all Participants Reach their End of Study Visit (see Section 6.4 'Derived Timepoints'), the Database is Locked, and the Sponsor Completes Authorization of Analysis Sets.

5 ANALYSIS SETS

Agreement and authorization of participants included and excluded from each analysis set will be conducted prior to database lock.

5.1 PROCESS FOR ANALYSIS SET ASSIGNMENT

The definitions of the analysis sets given below will be used to determine analysis set assignments. Analysis set assignments will be determined prior to Database Lock.

5.2 ENROLLED ANALYSIS SET [ENR]

The Enrolled Analysis Set (ENR) set will contain all participants who sign the ICF. The enrolled analysis set will be used to analyze participant disposition, inclusion/exclusion of analysis sets post-enrolment and exclusion criteria met and/or inclusion criteria not met for screen failures.

5.3 SAFETY ANALYSIS SET [SAF]

The Safety Analysis Set (SAF) will contain all participants who receive any amount of study drug (Fabrazyme) during study treatment period.

The safety analysis set will be used to analyze all safety and exploratory ADA endpoints.

Document: \\ieedc-

 $vnasc 01\BIOS data \Sanofi\Fabrazyme \IAB16602\Biostatistics \Documentation \SAP\SAP\Sanofi\Final \BIOS data \Sanofi\Fabrazyme \BIOS data \BIOS data \Sanofi\Fabrazyme \BIOS data \$

Version\lps17726-16-1-9-sap.docx

Author: Version Number: Final V1.0

Version Date: 22Oct2024

Template No.: CS_TP_BS016 Revision 7 Reference: CS_WI_BS005

Effective Date: 01Nov2021

Page 25 of 65

5.4 Intent-to-Treat Analysis Set [ITT]

The intent-to-treat analysis set (ITT) will contain all participants who were enrolled and allocated to study treatment.

The ITT analysis set will be used to evaluate all primary, secondary and the plasma lyso-GL3 (ng/mL) exploratory endpoint.

6 GENERAL CONSIDERATIONS

6.1 OBSERVATION PERIODS

- Pre-treatment period: The pre-treatment period is defined from when the participant provides informed consent up to the first dose of study intervention.
- Study treatment period: The study treatment period is defined as the time between the first dose of study intervention to the date of the last dose of study intervention. For Adverse Events, this is known as the Treatment Emergent (TE) period
- Post-treatment period: The post-treatment period is defined as the day after the last dose of study intervention until the last follow-up visit.

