1.2 Schema

Figure 1 Study Schema

Abbreviations: ADA = anti-drug antibody (ie, anti-agalsidase beta IgG antibody); AE = adverse event; AESI = adverse event of special interest; EOS = end-of-study; EOT = end-of-treatment; IAR = infusion associated reaction; lyso-GL3 = globotriaosylsphingosine; Q2W = every 2 weeks; SAE = serious adverse events; V = visit; W = week.

- a. V1 and V2 can take place on the same day. The number of visits during the Study Intervention Period (ie, Visits 2 to 10) may differ between participants, as those having a second IARs will discontinue the study intervention, and those who successfully reaches the shortest infusion duration planned for the cohort to which they belong will be considered as treatment completers. All participants will stay in the study for the follow-up visits at Week 12 and Week 28.
- b. IARs will be collected only during the Study Intervention Period which can be shorter than 16 weeks for some participants.

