1.3 Schedule of Activities

Table 1 Schedule of Activities

		Study Intervention Period: up to 16 Weeks ^b			EOS		
Procedure	Screening (Day -28 to Day 1)	Day 1	Q2W (± 3 days) Except Week 12	At Week 12 (± 3 days) Month 3	At Week 28 (± 3 days) Month 6	Notes	
		W0	W2, W4, W6, W8, W10, W14, W16	W12	W28		
	V1	V2	V3, V4, V5, V6, V7, V9, V10 °	V8	V11		
Written informed consent and participant's assent (when applicable)/assignment of participant identification number	X						
Inclusion and exclusion criteria	X						
Demography	Х					Including but not limited to age, gender, race/ethnicity, and duration of Fabrazyme treatment before entering the study.	
Medical history	X						
Current medical conditions	X						
Urine pregnancy test (only for WOCBC)	X					If a urine test cannot be confirmed as negative, a serum pregnancy test is required.	

		Study Intervention Period: up to 16 Weeks ^b			EOS	
Procedure	Screening (Day -28 to Day 1)	Day 1	Q2W (± 3 days) Except Week 12	At Week 12 (± 3 days) Month 3	At Week 28 (± 3 days) Month 6	Notes
		W0	W2, W4, W6, W8, W10, W14, W16	W12	W28	
	V1	V2	V3, V4, V5, V6, V7, V9, V10 °	V8	V11	
Vital signs and weight	X	X	X	X ^d		Vital signs include body temperature, heart rate, respiratory rate, and blood pressure., which will be assessed before and 1 hour after completion of each study intervention infusion. Refer to Sections 8.2 and 8.4.1.
Plasma Lyso-GL3		X	X	X	X	Blood sampling should be done prior to study intervention infusion. To be done at a central lab.
Serum for anti-agalsidase beta IgG antibody titers		X	X	X	X	Blood sampling should be done prior to study intervention infusion. To be done at a central lab.
Study intervention ^b		X	X	X		
IAR monitoring ^e		←				
AE monitoring		←				
SAE monitoring		←				
Concomitant medication review		←				

- Abbreviations: AE = adverse event; EOS = end-of-study; IAR = infusion associated reaction; IgG = immunoglobulin G; lyso-GL3 = globotriaosylsphingosine; Q2W = every 2 weeks; SAE = serious adverse event; V = visit; W = week; WOCBP = women of childbearing potential.
- a. The Screening Visit (V1) and Day 1 Visit (V2) can take place on the same day. If that occurs, the procedures planned for both visits should be performed only once, and all the screening procedures must be completed prior to the infusion and other study-required procedures.

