- b. The Study Intervention Period duration (up to 16 weeks) will depend on the participant's tolerability of the continuous reduction of the infusion duration time. When the participant successfully reaches the shortest infusion duration planned for the cohort which he/she belongs to, he/she will be considered a treatment completer and will not receive any further infusion as part of the study. The study intervention will be permanently discontinued if the participant presents a second IAR.
- c. Participants may have a different number of visits during the Study Intervention Period. Visits 1, 2, 3, 8 and 11 should happen regardless of the number of infusions a participant receives. All other visits are planned but will occur only if the participant does not present any criteria to permanently discontinue the study intervention, such as having a second IAR, or only until the treatment is not considered completed.
- d. Applicable only if the study intervention is administered in this visit. Refer to footnote b.
- e. IAR monitoring will be performed only during the Study Intervention Period which can be shorter than 16 weeks for some participants.
- Note: If a participant is not able to visit the study site for any reason, they should contact the study site by telephone. Adverse event and concomitant medication details may be collected during a telephone call. It may not be possible to collect all clinical laboratory samples or conduct clinical assessments during this time, but any details should be recorded in the source document and electronic case report form (eCRF). If alternative arrangements can be agreed for the sample collection or clinical assessments, the details should be documented in the eCRF.

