	Treatment : Fabrazyme 1 mg/kg Q2W up to the rate tolerated (refer to Section 6.2), with oral premedications given 30 minutes prior to each infusion.
	Endpoint : Binary, calculated separately for each infusion duration: Participant achieved infusion duration without experiencing any IAR.
	Intercurrent events: A while-on-treatment approach will be applied. Participants never observed to tolerate any infusion rate will be counted as not achieving the required duration for the infusion. A treatment policy approach will be applied in case pre-medications are not given as described within the protocol. No action will be taken for this event for the analysis even when pre-medications are not given as described within the protocol.
	Summary measure : For each infusion duration, number and % of participants achieving the endpoint.

Objectives	Estimand Description/Endpoints	
	Population : Participants with confirmed diagnosis of FD, age 2 to 65 years, Fabrazyme-experienced, treated for at least 3 months without IARs during the most recent 3 infusions.	
	Treatment : Fabrazyme 1 mg/kg Q2W up to the rate tolerated (refer to Section 6.2), with oral premedications given 30 minutes prior to each infusion.	
	Endpoint : Binary, calculated separately for each infusion duration: Participant achieved infusion duration without experiencing a second IAR.	
	Intercurrent events: A while-on-treatment approach will be applied. Participants never observed to tolerate any infusion rate will be counted as not achieving the required duration for the infusion. A treatment policy approach will be applied in case pre-medications are not given as described within the protocol. No action will be taken for this event for the analysis even when pre-medications are not given as described within the protocol.	
	Summary measure: For each infusion duration, number and % of participants achieving the endpoint.	
Exploratory		
To investigate the influence of increased infusion rate on the immunogenicity and efficacy of	Changes of plasma lyso-GL3 from baseline to 6 months follow-up	
Fabrazyme treatment	Change of the titer of ADA to Fabrazyme over 6 months follow-up	
Safety		
To investigate the influence of increased infusion rate on the safety of Fabrazyme treatment	Number, severity, and nature of AEs including IARs	

Abbreviations: ADA = anti-drug antibody, AE = adverse event; FD = Fabry disease; IAR = infusion associated reaction; lyso-GL3 = globotriaosylsphingosine; Q2W = every 2 weeks.

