8.5.1 Time Period and Frequency for Collecting AE and SAE Information

All AEs and SAEs will be collected from the signing of the ICF until the last scheduled visit at the time points specified in the SoA (Section 1.3).

All SAEs and AESIs will be recorded and reported to the Sponsor or designee immediately and under no circumstance should this exceed 24 hours of the Investigator's awareness of the event, as indicated in Section 10.3. The Investigator will submit any updated SAE or AESI data to the Sponsor or designee within 24 hours of their awareness of the updated information.

Investigators are not obligated to actively seek information on AEs or SAEs after conclusion of the study participation. However, if the Investigator learns of any SAE, including a death, at any time after a participant has been discharged from the study, and he/she considers the event/cause of death to be reasonably related to the study intervention or study participation, the Investigator must promptly notify the Sponsor or designee.

The method of recording, evaluating, and assessing causality of AE, AESI and SAE and the procedures for completing and transmitting safety reports are provided in Section 10.3.

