9.3 Statistical Analyses

9.3.1 General Considerations

All analyses, summaries, and listings will be performed using SAS® software (version 9.4 or higher) unless otherwise noted. All details regarding the statistical analysis and the preparation of tables, listings and figures will be described in the SAP.

The analysis of complete data for the study will be performed when all the participants have either completed the study or discontinued early from the study, all data from the study are in the database, and the database is locked.

In general, descriptive statistics of efficacy and safety parameters (result and change from baseline) by scheduled visits will be provided on observed cases, ie, inclusion of only participants having non-missing assessments at a specific visit. The data will be summarized per cohort and by pooled cohorts as described in Sections 9.3.2, 9.3.3 and 9.3.4, and where appropriate, per infusion duration.

The observation period of safety data will be as follows:

• Pre-treatment period: The pre-treatment observation period is defined from the signed informed consent up to the first dose of study intervention.

• Treatment Emergent (TE) period: The TE period is defined as the time from the first dose of study intervention to the last dose of study intervention + follow-up period.

The following descriptive statistics will be used as applicable to summarize the study data unless otherwise specified:

- Continuous data will be summarized using the number of observations available (n, mean, standard deviation [SD], minimum, median, 1st quartile, 3rd quartile, and maximum).
 Additionally, for the absolute change or percent change from baseline analysis, a 95% confidence interval (CI) will be provided.
- Categorical data will be summarized using count and percentage (the percentage of
 participants in each category relative to the total number of participants in the relevant
 analysis set or relative to the total number of participants in the relevant analysis set, with
 assessments available [where appropriate]) in each category. A 95% CI will be provided
 for the binary endpoint as appropriate. The change from baseline in distribution for the
 categorical endpoint will be presented with a shift table; number and percentage of
 participants will be provided.

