9.3.5 Safety Analysis

Safety endpoints include treatment-emergent adverse events, AESI (IARs and anaphylaxis), and vital signs.

For applicable safety variables, both the actual value and the change from the baseline value will be summarized at each visit using the n, mean, SD, median, minimum value, and maximum value. AEs and IARs will be summarized by frequency counts and percentage. Duration of exposure to study intervention and number of injections will be summarized descriptively.

All safety analyses will be performed on the Safety Analysis Set.

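### The SAP ends the treatment-emergent period at the last study infusion while the protocol adds follow-up, so later SAEs and some AE-related treatment stops miss the SAE and withdrawal outputs

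*SAP*

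**What the plan says.** Protocol 9.3.1 defines the TE period as the time "from the first dose of study intervention to the last dose of study intervention + follow-up period". Protocol 9.3.5 builds on it: "Safety endpoints include treatment-emergent adverse events, AESI (IARs and anaphylaxis), and vital signs". The safety endpoint in Table 2 of Protocol 3.0 is "Number, severity, and nature of AEs including IARs". Collection matches the long window (Protocol 8.5.1): "All AEs and SAEs will be collected from the signing of the ICF until the last scheduled visit".

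SAP 6.1 defines a study treatment period from first dose to the date of last dose and states: "For Adverse Events, this is known as the Treatment Emergent (TE) period". SAP 16.1 applies that cut by start date: up to and including the last infusion date is treatment-emergent, and later is post-treatment.

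In SAP 16.1.8 the overview and the intensity, relationship, SAE, AESI and permanent-discontinuation tables are limited to treatment-emergent events, as is the SAE listing. Post-treatment AEs get one table by system organ class and preferred term, and one listing.

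SAP 1 says that changes from the protocol's statistics are set out in Section 3.3. The legible entries there concern ADA and lyso-GL3, confidence intervals and shift tables, and the pooling of cohorts.

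**The concern.** The two definitions cannot both hold if follow-up has any length. The difference reaches a protocol safety endpoint in a study whose primary objective is safety and tolerability.

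The last study infusion is also the fastest one for a participant who reaches the target, so delayed events after it bear on the study question. A reader could see an empty SAE table and an empty SAE listing although an SAE occurred and was recorded. The withdrawal table and the disposition table could also give different numbers of AE-related treatment stops.

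**Working it through.** The plan gives no figure on this point to reproduce. The check has two parts.

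**Which outputs miss which events**

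- *Post-treatment SAE.* The SAE tables and the SAE listing are treatment-emergent only. An SAE with a known start date after the last infusion date is in neither. It appears in the post-treatment table and listing.
- *AE between infusions that ends treatment.* Dosing is every 2 weeks. If the AE starts after an infusion day and no further infusion is given, its start date is later than the last infusion date. SAP 16.1.5 counts only TEAEs with the action Drug Withdrawal, so it is left out. SAP 9.1 still summarises the reason for stopping treatment, so the two counts can differ.
- *AE that starts on the last infusion day and later becomes serious.* SAP 16.1 says such an AE gets a new record and that each record's own start date is used. It does not say that this start date is the date of worsening. If it is, the serious record is post-treatment and the SAE table misses it.
- *AE with a missing start date.* SAP 20.1 makes it a TEAE unless its stop date precedes the first dose. The problem is therefore confined to known later start dates.

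**Days moved from TE to post-treatment**

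Inputs:

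- Infusion visits after Day 1 are "W2, W4, W6, W8, W10, W14, W16" plus Week 12 (Protocol 1.3), so Week 16 is the last planned infusion.
- Participants who stop infusions early remain under observation: "All participants will stay in the study for the follow-up visits at Week 12 and Week 28".
- Assumption: the protocol's follow-up period ends at Week 28. Protocol 9.3.1 does not give its length. SAP 6.1 and 6.4 run post-treatment observation to the last follow-up visit, at 28 weeks.
- SAP 6.2 adds 1 to the date difference, so nominal Week *w* is Day 7*w* + 1, and Week 28 is Day 197.

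Formula: days moved = 197 − (7*w* + 1), and share = days moved / 197.

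- Last infusion at Week 16 (Day 113): 197 − 113 = 84; 84/197 = 42.6%.
- Week 8 (Day 57): 197 − 57 = 140; 140/197 = 71.1%.
- Week 6 (Day 43): 197 − 43 = 154; 154/197 = 78.2%.
- Week 2 (Day 15): 197 − 15 = 182; 182/197 = 92.4%.
- Only one infusion (Day 1): 197 − 1 = 196; 196/197 = 99.5%.

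Weeks 8 and 6 are illustrative. They are the completion times without an IAR given in the rationale column of Protocol 10.6, for starting durations of 120 and 90 minutes. They are not bounds, because SAP 15.2.1.2 allows a planned starting duration under 90 minutes. Week 2 is the earliest stop under the rule "The study intervention will be permanently discontinued if the participant presents a second IAR", with IARs at both of the first two infusions. Stopping after one infusion is possible on other grounds in Protocol 7.1.

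With the ±3 day windows, the Week 16 case runs from (194 − 116)/194 = 78/194 = 40.2% to (200 − 110)/200 = 90/200 = 45.0%. If follow-up ended before Week 28, the days moved would fall one for one.

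**The case against.** The strongest defence is that nothing disappears. Later AEs have their own table and listing, and SAP 7.3.2.2.1 and 7.3.2.2.2 keep collected intensity and causality in that listing. Deaths are listed for the whole study, and reasons for stopping treatment are summarised and listed. IARs must occur on the infusion day, so they are unaffected, as are the primary and secondary endpoints. All of this stands, and it means the events are reclassified rather than lost. The output templates named in SAP 8 are not among the documents and may add detail, such as a seriousness flag.

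A second defence is that a narrow window is reasonable. Protocol 6.7 leaves treatment after the study infusions to the investigator or treating physician, so follow-up may include routine-care infusions. That is a fair reason, but the legible SAP text does not give it. It also does not explain why an SAE on the day after the last study infusion should be missing from the SAE outputs. A cut at one dosing interval would not separate the two sources cleanly either: if routine care kept a similar ±3 day tolerance, an infusion could fall on day 11 to 14.

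Two stronger readings are tempting. One is that the SAP changed the definition without declaring it. Part of Table B in SAP 3.3 did not survive text extraction, so only the absence of a legible entry can be stated. The other is that 43% or more of adverse events would be misplaced. The percentages are shares of calendar days, and the documents give no event rate.

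**Conclusion.** The conflict between Protocol 9.3.1 and SAP 6.1 and 16.1 is real, and the incomplete SAE and withdrawal outputs follow from the SAP as written. It should be fixed. A declaration in SAP 3.3, even if one exists in the lost text, would not by itself fill the gaps in those tables.

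The days moved are at least 84 of 197 (43%) for a participant whose last infusion is at nominal Week 16 or earlier, given follow-up to Week 28. How many events this affects is unknown. The documents do not show that the protocol's window is the only defensible one, so the requirement is to reconcile the two and make the affected outputs complete. The effect on AEs that worsen after the last infusion day is conditional on how new records are dated.

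**What to change.** Reconcile SAP 6.1 and 16.1 with Protocol 9.3.1 in one of two ways:

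- adopt the protocol window for AEs only, leaving the study treatment period unchanged for endpoints, medications, lyso-GL3 and ADA sampling, and vital signs; or
- keep the narrower window, and declare and justify it in SAP 3.3.

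In either case:

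- make the SAE table and SAE listing cover all SAEs from first dose to end of study, flagged by whether they start up to or after the last study infusion date;
- count AEs with the action Drug Withdrawal regardless of TE status;
- summarise intensity and relationship for AEs that start after the last study infusion;
- state in SAP 16.1 which start date a new record for a worsened or serious AE carries.

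The cost is SAP wording, a few changed or added outputs and programming; no new data are needed. Counts may include events under routine-care infusions, which the period flag makes visible. If the protocol window is adopted, a missing causality in follow-up would change from not related to related under SAP 7.3.2.2.2. The SAP should say whether that is intended. The second route avoids that change.
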